**IND 118,458 Sponsor: [name], M**

## SCHEMA

## Prior Study Population Immunotherapy Alone

- After a subject has completed 6 months of nivolumab (regardless of arm assignment), they can receive nivolumab every 4 weeks instead of every 2 weeks.

The goal of this study is to assess whether 6 cycles of concurrent epigenetic therapy consisting of azacitidine and entinostat in combination with nivolumab can increase response compared to nivolumab single agent in patients who are immunotherapy naïve (Arm D), or in patients whose disease has progressed on immunotherapy when compared to historical single agent docetaxel (Arms E & F).

Primary endpoint is the response rate by treatment Arm. Response will be assessed from first dose of trial therapy.

Patients experiencing significant toxicities on Arm D during cycles 1-6 of combination therapy of azacitidine, entinostat and Nivolumab may proceed to Nivolumab only. Otherwise, patients whose disease is responding, progressing, or stable on combination therapy with Nivolumab, azacitidine and entinostat will proceed to Nivolumab monotherapy after 6 cycles. Patients experiencing significant toxicities due to nivolumab or documented disease progression (see **Section 9**) on Arm E or Arm F during cycles 1-6 of combination therapy of azacitidine, entinostat and Nivolumab must come off study treatment. Patients whose disease is responding or stable on combination therapy with Nivolumab, azacitidine and entinostat will proceed to Nivolumab monotherapy after 6 cycles on Arms E and F.

We plan to enroll up to 20 patients each on Arms D, E and F (N=60). Allowing for up to 10% unevaluable patients, we will enroll up to 22 patients on each Arm (D-F), or a total of 66.

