## 1. OBJECTIVES

### 1.1 Primary Endpoint

#### 1) Objective response rate

Objective response to combination Nivolumab and epigenetic therapy will be assessed by Arm. Response will be assessed by RECIST 1.1 criteria, baseline scans for this assessment will be done within 4 weeks of enrollment.

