### 10.4 Interim Analyses

The study design calls for interim futility analysis by arm. These analyses will occur separately by arm once 10 patients are on an arm and have either received at least 6 cycles of therapy or experienced a PFS event. Subsequent analyses will occur after 15 patients have either received at least 6 cycles of therapy or experienced a PFS event. The final analysis will occur after 20 patients have entered and received full therapy (6 cycles). The futility analysis is based on Bayesian hypothesis testing.

For Arm D, we take the expected ORR to be 20% if epigenetic therapy does not increase the clinical effectiveness of nivolumab alone. This estimate is based on results of the Checkmate studies (CheckMate 057 (non-squamous NSCLC) ORR = 19%; CheckMate017 (squamous cell NSCLC) ORR = 20%). We would consider the addition of epigenetic therapy encouraging if the ORR is 35% or higher. The study will stop for futility if we see 0 responses among the first 10 patients or no more than 1 response in the first 15 patients. We will not consider this Arm promising if we see 3 or fewer responders out of 20 patients. The following table provides the operating characteristics for Arm D based on 5000 simulations.

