#### Simulation Results for Arm D

| Scenario | Assumed true response rate | Pr(Stop for inferiority) | Average # patients treated (10%, 25%, 50%, 75%, 90%) |
|----------|----------------------------|--------------------------|--|
| 1        | 0.1                        | 0.876                    | 15.4 (10, 10, 15, 20, 20 )                           |
| 2        | 0.15                       | 0.662                    | 17.3 (10, 15, 20, 20, 20 )                           |
| 3        | 0.2                        | 0.434                    | 18.51 (10, 20, 20, 20, 20 )                          |
| 4        | 0.25                       | 0.243                    | 19.25 (20, 20, 20, 20, 20 )                          |
| 5        | 0.3                        | 0.119                    | 19.61 (20, 20, 20, 20, 20 )                          |
| 6        | 0.35                       | 0.047                    | 19.86 (20, 20, 20, 20, 20 )                          |
| 7        | 0.4                        | 0.021                    | 19.92 (20, 20, 20, 20, 20 )                          |
| 8        | 0.45                       | 0.008                    | 19.96 (20, 20, 20, 20, 20 )                          |
| 9        | 0.5                        | 0.002                    | 19.99 (20, 20, 20, 20, 20 )                          |

For Arms E and F, respectively, we take the expected ORR to be virtually 0% if epigenetic therapy does not increase the clinical effectiveness of nivolumab alone. We would consider the addition of epigenetic therapy encouraging if the ORR is at least 10%. The study will stop for futility if we see 0 responses among the first 15 patients. We will not consider an

Arm promising if none of the 20 patients on that Arm responds. The following table provides the operating characteristics for Arms E and F, respectively, based on 5000 simulations.

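### The Schema sets Arms E and F against historical docetaxel, but Section 10.4 judges them only against virtually 0% for nivolumab alone, and no docetaxel response rate is given

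*Combined protocol and SAP*

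**What the plan says.** The Schema's goal paragraph gives each population its own comparator. For Arm D it is single-agent nivolumab. For Arms E and F the question is whether response increases "in patients whose disease has progressed on immunotherapy when compared to historical single agent docetaxel (Arms E & F".

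Section 10.4 then sets the E/F reference differently: "we take the expected ORR to be virtually 0% if epigenetic therapy does not increase the clinical effectiveness of nivolumab alone". The target is "We would consider the addition of epigenetic therapy encouraging if the ORR is at least 10" per cent. The interim rule is "The study will stop for futility if we see 0 responses among the first 15 patients". At the end, the plan will not consider an "Arm promising if none of the 20 patients on that Arm responds".

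The other places that could carry a docetaxel comparison do not. Section 1.1 says only "Objective response to combination Nivolumab and epigenetic therapy will be assessed by Arm". Section 10.1.1 describes identifying response in three patient groups. Section 10.2 makes the final analysis of each arm descriptive, with summary statistics and confidence intervals. In the supplied text, docetaxel otherwise appears only in two reference titles (22 and 23), and no docetaxel response rate is stated.

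**The concern.** The goal and the decision rule answer different questions. Arm D shows what a usable benchmark looks like: Section 10.4 gives a nivolumab-alone rate of 20%, sources it to two trials (19% and 20%), and sets the target beside it ("We would consider the addition of epigenetic therapy encouraging if the ORR is 35% or higher"). Arms E and F have no such figure for the comparator named in their own goal.

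What is at stake is interpretation. If an E/F arm passes, the Schema invites the question whether it did better than docetaxel, and nothing in the plan can answer it. The futility rule was not built for that comparison, and the planned interval has no docetaxel rate to be set beside. The gap would then have to be filled after the data are known, by choosing a historical rate at the time of reporting.

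**Working it through.** **Inputs.** Section 10.4: stop at 0/15, not promising at 0/20, reference virtually 0%, target at least 10%. Section 10.2: 20 patients per arm, descriptive final analysis. Docetaxel response rate: not given, so 5%, 10% and 15% are assumed below only to show the range.

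**1. Reproduce the printed E/F table.** With true response rate p, the chance of stopping at 0/15 is (1 − p)^15, and the mean number treated is 15 × stop + 20 × (1 − stop).

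| True rate | (1 − p)^15 | Printed stop | Mean N, computed | Mean N, printed |
|---|---|---|---|---|
| 2.5% | 0.684 | 0.683 | 16.58 | 16.58 |
| 5% | 0.463 | 0.462 | 17.68 | 17.69 |
| 10% | 0.206 | 0.206 | 18.97 | 18.97 |
| 15% | 0.087 | 0.085 | 19.56 | 19.58 |

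The remaining rows agree equally well. The table is right, and it is the table of the 0/15 rule.

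**2. The rule against its own reference.** The chance of clearing is 1 − (1 − p)^15. It is 0 at a true rate of 0%, 1.5% at 0.1%, 7.2% at 0.5% and 14.0% at 1%. Against a reference of virtually 0%, the rule behaves sensibly.

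**3. The rule against docetaxel.** Suppose an arm is no better than docetaxel, so its true rate equals the docetaxel rate:

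- docetaxel 5% (assumed): 1 − 0.95^15 = 1 − 0.4633 = 0.537, or 54%
- docetaxel 10% (assumed): 1 − 0.90^15 = 1 − 0.2059 = 0.794, or 79%
- docetaxel 15% (assumed): 1 − 0.85^15 = 1 − 0.0874 = 0.913, or 91%

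Over this range, an arm with no advantage over docetaxel clears more often than not. Clearing therefore says little about the comparison in the Schema.

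**4. Side note on the 0/20 bar.** A count of 0/20 requires 0/15 first, where the arm has already stopped. When responses are counted the same way at both analyses, the final bar adds no stop at any response rate. A 0/20 rule alone would give stop probabilities of 0.603, 0.359 and 0.122 at 2.5%, 5% and 10%, which are not the printed figures.

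**The case against.** The strongest reply is that Section 10.4 is a futility screen and was never offered as a test against docetaxel. Its language is about futility, promise and encouragement, not superiority, and Section 10.2 openly makes the final analysis descriptive. A confidence interval can be read against a historical rate, so all that is missing is one figure and a sentence on its use. Nor is virtually 0% an odd reference: Section 3.1.11.2 requires E/F patients to be, in the investigator's opinion, unlikely to benefit from nivolumab alone.

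Most of this stands, and it limits the point. The boundaries are coherent for their own purpose. But it does not remove the mismatch: the missing figure and sentence are exactly what the Schema goal needs, and nothing in the supplied text reconciles the two comparators.

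Some stronger readings are tempting and should not be drawn:

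- *The redundant 0/20 bar damages the design.* It does not. It changes no stop probability, sample size or result.
- *The 10-patient look is empty for E/F.* Section 10.4 says "These analyses will occur separately by arm once 10 patients are on an arm" and gives E/F no response boundary there. But Section 10.5 applies the feasibility rule at each interim analysis, with a printed boundary of 6 of 10.
- *Confirmation of response is left open.* Section 10.1.2 refers response to Section 9, and the best-response table in 9.1.4.3 applies confirmation to non-randomized trials with response as the primary endpoint.
- *Twenty patients are too few to exclude a docetaxel rate.* Section 10.2 sets neither an interval level nor a superiority criterion, so any such calculation would hold the plan to a bar that it did not set.

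**Conclusion.** The concern holds as a mismatch of comparators. The Schema asks whether Arms E and F improve on historical docetaxel. Section 10.4 asks whether they show any response where almost none is expected from nivolumab alone. Without a docetaxel rate, the stated goal cannot be answered by the plan as written.

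The size depends on a figure that the documents do not give. Over an assumed docetaxel rate of 5% to 15%, an arm with no advantage clears with probability 54% to 91%. This assumes independent patients with a common true response rate and the same counting of responses throughout.

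A reader might infer that the futility rule or its simulation table is wrong, or that the plan claims superiority over docetaxel for an arm that clears. The documents support neither: the table reproduces, the rule suits its own reference, and Section 10.4 makes no superiority claim. One limit applies: some front pages and the figures are absent from the supplied text, so the statement that no docetaxel rate is given refers to the text available.

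**What to change.** Use one comparator for Arms E and F in both the Schema and Section 10.4. There are two ways to do it:

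1. Restate the Schema goal for E/F as showing activity beyond the negligible response (virtually 0%) expected from nivolumab alone after progression on immunotherapy. Add a sentence to Section 10.4 that clearing the futility bars is not evidence of improvement over docetaxel.
2. Keep docetaxel. State its historical response rate, justify it for patients already treated with PD-1/PD-L1 agents, and say in Section 10.2 or 10.4 that the E/F confidence interval will be read against it.

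Either way, Section 10.4 could note in passing that the 0/20 bar adds no stop beyond 0/15 and that the 10-patient look carries only the feasibility rule for E/F, if that is what was intended.

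The cost is wording: no patients, looks or boundaries change. The first option gives a more modest E/F conclusion with no docetaxel claim. The second needs an outside rate that the sponsor must find and defend.

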#### **4.4 Duration of Therapy**

Arm D: Epigenetic therapy (azacitidine and entinostat) in combination with nivolumab will be given for six 28-day cycles on this protocol. Patients experiencing adverse event(s) that in the view of the treating physician or principal investigator make six cycles undesirable, may continue with Nivolumab as a single agent after only 2 cycles of concurrent epigenetic therapy with Nivolumab. Please see section 4.4.1 regarding treatment at time of progressive disease (PD).

Arm E and Arm F: Epigenetic therapy (azacitidine and entinostat) in combination with nivolumab will be given for six 28-day cycles on this protocol. Patients experiencing adverse event(s) that in the view of the treating physician or principal investigator make six cycles undesirable, may continue with Nivolumab as a single agent after only 2 cycles of concurrent epigenetic therapy with Nivolumab. Please see section 4.4.1 regarding treatment at time of progressive disease (PD).

Nivolumab monotherapy on all Arms may continue until one of the following criteria applies and at that time, nivolumab treatment will be permanently discontinued:

- Any Grade  $\geq 2$  drug-related uveitis, eye pain or blurred vision that does not respond to topical therapy and does not improve to Grade 1 severity within the re-treatment period OR requires systemic treatment
- Any Grade 3 non-skin, drug-related adverse event lasting  $> 7$  days, with the following exceptions for laboratory abnormalities, drug-related bronchospasm, hypersensitivity reactions, and infusion reaction:
  - Grade 3 drug-related bronchospasm, hypersensitivity reaction, or infusion reaction of any duration requires discontinuation
  - Grade 3 drug-related laboratory abnormalities do not require treatment discontinuation except:
    - Grade 3 drug-related thrombocytopenia  $> 7$  days or associated with bleeding requires discontinuation
    - Any drug-related liver function test (LFT) abnormality that meets the following

criteria require discontinuation:

- AST or ALT > 5-10x ULN for > 2 weeks
- AST or ALT > 10x ULN
- Total bilirubin > 5x ULN
- Concurrent AST or ALT > 3x ULN and total bilirubin > 2x ULN

- Any Grade 4 drug-related adverse event or laboratory abnormality, except for the following events which do not require discontinuation:
  - Grade 4 neutropenia  $\leq$  7 days
  - Grade 4 lymphopenia or leucopenia

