#### **4.4.1 Treatment Beyond Disease Progression**

Treatment beyond disease progression is allowed for patients receiving concurrent azacitidine, entinostat and nivolumab on Arm D, Arm E and Arm F. If disease progression (PD) is noted during the 6 cycles of concurrent therapy per RECIST 1.1, the patient may continue study treatment until disease progression is confirmed. If at that time disease progression (PD) is confirmed, the patient will come off study treatment. After 6 concurrent cycles, patients will continue nivolumab monotherapy treatment irrespective of disease

progression status, and will follow the decision to treat beyond disease progression (PD) as per below. If the noted PD requires palliative radiation therapy, please see Section 4.2.12 regarding subsequent study treatment.

Subjects being currently treated with nivolumab monotherapy on any study Arm will be permitted to continue treatment beyond initial RECIST 1.1 defined PD as long as they meet the following criteria:

1. Investigator-assessed clinical benefit, and do not have rapid disease progression
2. Continue to meet all other study protocol eligibility criteria
3. Tolerance of the study drug
4. Stable performance status
5. Treatment beyond progression will not delay an imminent intervention to prevent serious complications of disease progression (e.g. CNS metastasis)

The decision to continue treatment beyond initial progression must be documented in the study records.

A radiographic assessment/scan will be performed at the end of the cycle following the original PD to determine whether there has been a decrease in the tumor size or continued PD. The assessment of clinical benefit should be balanced by clinical judgment as to whether the subject is clinically deteriorating and unlikely to receive any benefit from continued treatment with nivolumab.

If the investigator feels that the patient receiving nivolumab monotherapy continues to achieve clinical benefit by continuing treatment, the subject may remain on the trial and continue to receive monitoring according to the Study calendar.

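### The Schema and Section 4.4.1 give inconsistent instructions on study treatment after progression, chiefly for Arm D patients whose progression is confirmed during cycles 1–6

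*Combined protocol and SAP*

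**What the plan says.** The Schema figure is not reproduced in the text, so this point rests on the Schema's prose.

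- **Schema, Arm D.** After the Arm D toxicity rule, the Schema states that "patients whose disease is responding, progressing, or stable on combination therapy with Nivolumab, azacitidine and entinostat will proceed to Nivolumab monotherapy after 6 cycles". It gives no progression exit for this arm in cycles 1–6.
- **Schema, Arms E and F.** Patients with significant nivolumab toxicity or documented progression (with a reference to Section 9) "on Arm E or Arm F during cycles 1-6 of combination therapy of azacitidine, entinostat and Nivolumab must come off study treatment". For what follows cycle 6: "Patients whose disease is responding or stable on combination therapy with Nivolumab, azacitidine and entinostat will proceed to Nivolumab monotherapy after 6 cycles". Progressing patients are not in that list.
- **Section 4.4.1, all three arms.** "Treatment beyond disease progression is allowed for patients receiving concurrent azacitidine, entinostat and nivolumab on Arm D, Arm E and Arm F". A patient with progression noted in the six cycles may continue until it is confirmed, and then: "If at that time disease progression (PD) is confirmed, the patient will come off study treatment". The next sentence reads "After 6 concurrent cycles, patients will continue nivolumab monotherapy treatment irrespective of disease" progression status, and makes this subject to the rules that follow. Those rules are five conditions for treating beyond progression, plus documentation of the decision.
- **Other sections.** Section 4.4 (for each arm), Section 4.6 and Section 9.1 refer progression to Section 4.4.1. Section 10.1.1.1 has nivolumab given until confirmed progression.

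**The concern.** The Schema sets arm-specific rules: *progressing* appears in the Arm D sentence, and the Arm E/F sentences replace it with a mandatory exit. Section 4.4.1 sets one rule for all three arms. Both are written as instructions, and nothing says which prevails.

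Section 10.7 describes a multi-institutional study. A site working from the Schema and one working from Section 4.4.1 could give different amounts of study drug to patients in the same state. That bears on patient exposure after confirmed progression and on the toxicity tables planned in Section 10.6.

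**Working it through.** **Inputs**
- Combination phase: six 28-day cycles (Section 4.4).
- Scans: every 8 weeks, ±1 week (Section 8, Arms D–F calendar, footnote 6).
- Confirmation of progression: at the next scheduled scan 8 weeks later, no sooner than 4 weeks (Section 9.1).
- Doses per combination cycle (Section 4.1): azacitidine on days 1–5 and 8–10, 5 + 3 = 8; entinostat 2; nivolumab 2.

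**Timeline.** 6 × 28 / 7 = 24 weeks, which reproduces the figure in Section 10.5. Scans fall at weeks 8, 16, 24 and 32. The week-24 scan can fall from 24 − 1 = 23 to 24 + 1 = 25.

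**Leg 1: Arm D, progression confirmed in cycles 1–6.** Combination cycles remaining after confirmation = (24 − confirmation week) / 4.

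| First PD | Confirmed | Cycles remaining | Azacitidine / entinostat / nivolumab doses |
|---|---|---|---|
| Week 8 | Week 12 | (24 − 12)/4 = 3 | 24 / 6 / 6 |
| Week 8 | Week 16 | (24 − 16)/4 = 2 | 16 / 4 / 4 |
| Week 16 | Week 20 | (24 − 20)/4 = 1 | 8 / 2 / 2 |
| Week 16 | Week 24 | (24 − 24)/4 = 0 | none; see leg 3 |

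Under Section 4.4.1 the patient leaves study treatment at confirmation. These rows are therefore the difference if the Schema is taken to keep the patient on to cycle 6. If the Schema is taken to say nothing about an earlier exit, the difference in combination cycles is 0 in every row.

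**Leg 2: Arms E and F.** The result turns on the word *documented*.
- *If it means confirmed.* The Schema's reference to Section 9, which calls for confirmation, supports this. The Schema and Section 4.4.1 then agree within cycles 1–6. What remains is the end of cycle 6. Progression first seen at week 24 is not confirmed until week 24 + 4 = 28 to 24 + 8 = 32. Section 4.4.1 continues such a patient subject to its conditions; the Schema does not list the patient as proceeding, though it does not say that only the listed patients proceed.
- *If it means first seen.* The footnote to the Section 4.1 regimen table speaks of a first documented PD after which nivolumab monotherapy may go on, which supports this. The Schema then ends treatment at first progression, while Section 4.4.1 allows it to continue until confirmation, 4 to 8 weeks later: 4/4 = 1 to 8/4 = 2 cycles.

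Sections 4.4.1 and 4.6 use *confirmed*, so the vocabulary does not settle the matter.

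**Leg 3: within Section 4.4.1 (minor).** Progression first seen at week 16 and confirmed at the next scheduled scan is confirmed in weeks 23–25, on either side of the end of cycle 6. Two adjacent sentences could then apply: off treatment on confirmation, or monotherapy whatever the progression status. Section 4.4.1 also says "A radiographic assessment/scan will be performed at the end of the cycle following the original PD". If that applies during combination therapy, the scan would be at about week 16 + 4 = 20 and the overlap would not arise. The sentence follows the monotherapy criteria, so its reach is not clear.

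**Later monotherapy.** Section 4.4 says treatment must stop once the next assessment confirms progression. The last paragraph of Section 4.4.1 lets a patient judged to be benefiting remain on nivolumab. The two give no common end point.

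**The case against.** The strongest reply is that the Schema is a summary and its Arm D sentence only describes what happens after cycle 6. Read so, *progressing* matches Section 4.4.1's own continuation irrespective of progression status, and a patient with earlier confirmed progression has already left. Sections 4.4, 4.6, 9.1 and 10.1.1.1 all point toward Section 4.4.1. That reading is available and would bring the Arm D difference in combination cycles to 0. It is not written down, however, and the Schema gives an early progression exit to Arms E and F while giving none to Arm D.

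On leg 2, the end-of-cycle-6 part rests on the Schema's silence, so it is not a contradiction in itself. The sharper discrepancy, over *documented*, exists only under one of two readings.

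On leg 3, the reply largely succeeds. The exit in Section 4.4.1 is triggered by progression noted during the six cycles, and the following sentence can be read as covering those still on treatment. A reader might infer that Section 4.4.1 contradicts itself; the text supports only that the sequence is unstated at a point the routine scan schedule reaches.

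There are also safeguards. Monotherapy beyond progression is subject to five conditions and documentation, Section 6.7 requires reconsent, and Section 10.7 provides weekly telephone conferences. These reduce the risk of divergent practice but do not say which text governs.

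**Conclusion.** The inconsistency is real and should be corrected. It is firmest for Arm D, conditional on the meaning of *documented* for Arms E and F, and minor within Section 4.4.1.

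For Arm D the size is 0 to 3 combination cycles per affected patient, assuming the nominal scan dates and confirmation 4 to 8 weeks after first progression. A reader might infer that the Schema requires Arm D patients with confirmed progression to stay on the combination to cycle 6. It does not say so, and the upper figure holds only under that reading.

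A reader might also infer that the extra monotherapy is limited to the interval before the next scan. The documents do not support a limit, because Sections 4.4 and 4.4.1 differ on whether treatment ends there. They also give no rate of progression confirmed in cycles 1–6, so no count of affected patients is offered.

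Nor do the documents support reading this as a threat to the efficacy results. Best overall response is counted up to progression (Section 9.1.4.3). It, PFS and time to progression should not change provided progression is dated at first occurrence. Feasibility excludes progression and death (Section 10.5), and no sample size or operating characteristic depends on the point.

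**What to change.** Reconcile the Schema with Sections 4.4, 4.4.1, 4.6 and 9.1 so that each arm has one instruction for each of:

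1. first progression in cycles 1–6;
2. confirmed progression in cycles 1–6;
3. progression status at the end of cycle 6, including a confirmatory scan that falls in weeks 23–25.

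Use *documented* and *confirmed* consistently in the Schema, the Section 4.1 table footnote and Sections 4.4.1 and 4.6. Reconcile the monotherapy stopping text in Section 4.4 with the last paragraph of Section 4.4.1. State which section governs if the Schema differs. This review takes no position on which treatment rule is right; that is for the sponsor and investigators.

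The cost is amendment wording. Sample size and the planned statistical analyses are unchanged, and the reconciliation needs no added visits or assessments.
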